Impact of Diabetes Mellitus on Retinal Microvasculature in Patients without Clinical Retinopathy Using Optical Coherence Tomography Angiography

Study Protocol Submitted for Partial Fulfillment
of Master Degree in ophthalmology

Presented by

[name]

M.B.B.CH

Resident of Ophthalmology
Sohag University Hospital.

Supervised by

[name]

Professor of Ophthalmology
Faculty of Medicine, Sohag University

[name]

Assistant Professor of Ophthalmology
Faculty of Medicine, Sohag University.

[name]

Lecturer of Ophthalmology
Faculty of Medicine, Sohag University.

Sohag University
2024

Introduction

Diabetic retinopathy (DR) is a common microvascular complication of diabetes mellitus (DM) and is the leading cause of preventable blindness in working aged people [1].

Fluorescein angiography (FA) is the gold standard investigation for evaluation of Diabetic Retinopathy, yet it is time-consuming and requires invasive intravenous dye administration that may cause various reactions such as vomiting and urticaria [2].

The advent of Optical Coherence Tomography Angiography (OCTA) overcame these disadvantages and added value of imaging rapid and high-resolution images of the retinal microvasculature without intravenous dye administration [3, 4].

OCTA identifies features of preclinical retinopathy that are not detectable by clinical examination and evaluates early ischemic changes as enlarged foveal avascular zones (FAZ) [5-8] , reduced vessel density [8, 9] that are reported to present without clinical retinopathy and also microaneurysm formation which is the most common early clinically visible manifestation of DR [10].

Duration of diabetes has been reported to be a strong predictor for the progression of DR as persistent elevated blood glucose level gradually leads to weakening of the walls of small retinal blood vessels leading to tiny bulges and even leakage [11, 12].

Aim of the work

To assess the impact of duration of DM on OCTA parameters in diabetic patients without clinical Diabetic retinopathy.

Patients and Methods

Study design: Observational, Cross-sectional study.

Study setting: Sohag University Hospital, department of Ophthalmology.

Study population: patients will be recruited from diabetics who will present for retinopathy screening examination at outpatient clinic of Sohag University Hospital.

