Sample size determination: every group would include from 60 to 80 eyes calculated by Yamane's formula: $n = N / (1 + N) e^2$, where n = the sample size, N = the population of the study and e = the margin error in the calculation.

The study will be conducted after acquiring the approval of the Medical Research Ethics Committee in the Faculty of Medicine, Sohag University considering that all study participants will be carefully cognized with the nature, presentation and potential consequences of the disease, investigation options and importance of regular follow up and tight control by an informed consent.

Inclusion criteria:

- 1) Age : Above 40 years old
- 2) Type of DM: Type 2.
- 3) Fundus examination: no macular edema or other signs of clinical retinopathy.

Exclusion criteria:

- 1) Age : below 40 years old
- 2) Ocular history : any history of significant ocular injury or disease that could affect the retinal microvasculature such as retinal vascular occlusion, glaucoma, or vitreo-macular disease, as such conditions have also been noted to show sub-clinical OCTA changes [13, 14].
- 3) Fundus examination: macular edema or any other signs of clinical retinopathy.

Procedure: patients recruited for the study will be subjected to the following:

- Personal history: including name, age, sex, occupation and residency.
- Medical history: including duration of DM, type of DM, use of DM medications, most recent hemoglobin A1C and presence of comorbid diseases.
- Ocular examination: including extra-ocular examination, anterior segment examination, visual acuity assessment, IOP measurement and posterior segment examination.

Signs of diabetic retinopathy to be detected include; Micro-aneurysm, Dot and Blot hemorrhages, Flame-shaped splinter hemorrhages, Retinal edema and hard exudates, Cotton-wool spots, venous loops and venous and Intra-retinal microvascular abnormalities (IRMA).

Patients who meet the inclusion criteria will be divided into three groups depending on the duration of diabetes: 0–5 years (short), 6–10 years (medium), and more than 10 years (long). Fourth control group of patients who meet the criteria and don't have DM will be included.

OCTA images will be obtained for the patients by a comprehensive wide-field OCT device (Optovue RTVue XR 100 Avanti, Germany) with 6×6 mm field of view centered at the fovea.

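### The comparison of diabetic groups with non-diabetic controls is not protected against age or sex differences: no balancing is planned, the group tests are unadjusted, and the planned regression is not tied to it

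*Combined protocol and SAP*

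**What the plan says.** The title promises the "Impact of Diabetes Mellitus on Retinal Microvasculature in Patients without Clinical Retinopathy". The Aim of the work is narrower: "To assess the impact of duration of DM on OCTA parameters in diabetic patients without clinical Diabetic retinopathy".

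The Procedure section forms three duration groups and then adds: "Fourth control group of patients who meet the criteria and don't have DM will be included". The rest of the protocol bears on the controls as follows.

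- **Source.** The setting is the ophthalmology department. The Study population entry covers diabetics only: "patients will be recruited from diabetics who will present for retinopathy screening examination at outpatient clinic of Sohag University Hospital".
- **Eligibility.** The inclusion criteria give "Age : Above 40 years old" and "Type of DM: Type 2". There is no upper age limit, no age stratum and no condition on sex.
- **Data recorded.** "Personal history: including name, age, sex, occupation and residency", and in the medical history "most recent hemoglobin A1C and presence of comorbid diseases".
- **Size.** Each group, controls included, has 60 to 80 eyes, one eye per patient.
- **Analysis.** Statistical Analysis names Kruskal–Wallis or one-way ANOVA across groups, and Mann–Whitney or t-tests for pairs. It also plans a multivariate linear regression of each OCTA parameter on systemic risk factors, which it does not list, and a Bonferroni correction where judged appropriate.

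**The concern.** The control contrast is the only planned comparison of diabetics without retinopathy against people without diabetes, so it is what supports the title. None of the named group tests can adjust for age or sex. The regression might do so, but it lists no covariates and no group term, so adjustment is neither assured nor ruled out.

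If controls are younger than the diabetics and the OCTA measures change with age, a difference in vessel density or FAZ could appear without any diabetes effect. If controls are older, a real effect could be missed. Bonferroni makes false positives rarer but leaves the bias in the estimate.

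A separate drafting point: read literally, controls must meet criteria that include type 2 diabetes. The intended meaning, all criteria except diabetes, is easy to infer.

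**Working it through.** The plan gives no figure for this contrast to reproduce. The check asks how sensitive the unadjusted comparison is to an imbalance.

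**Inputs from the protocol:** n = 60 or 80 per group, four groups, two-sided 0.05.

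**Assumed inputs (not in the documents):** age SD 9 years; OCTA–age correlation r = 0.2 to 0.3; no true diabetes effect; Bonferroni over all six pairs of groups, 0.05/6 = 0.83%.

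**Step 1: bias.** In outcome SDs, bias d = r × gap / 9. For a 5-year gap, 0.2 × 5/9 = 0.11 and 0.3 × 5/9 = 0.17.

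**Step 2: false-positive rate of one duration group against controls.** The t statistic has noncentrality d/√(2/n), where √(2/60) = 0.183 and √(2/80) = 0.158. At 5 years this is 0.61 to 0.91 (n = 60) or 0.70 to 1.05 (n = 80). Each cell below gives r = 0.2 / r = 0.3.

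| Age gap | n = 60, at 5% | n = 80, at 5% | n = 60, at 0.83% | n = 80, at 0.83% |
|---|---|---|---|---|
| 2 years | 5.7 / 6.5% | 5.9 / 7.0% | 1.0 / 1.3% | 1.1 / 1.4% |
| 3 years | 6.5 / 8.4% | 7.0 / 9.6% | 1.3 / 1.9% | 1.4 / 2.3% |
| 5 years | 9.3 / 14.8% | 10.8 / 18.2% | 2.1 / 4.1% | 2.6 / 5.5% |
| 8 years | 16.2 / 30.5% | 20.1 / 38.9% | 4.7 / 11.5% | 6.4 / 16.6% |

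**Step 3: any of the three control contrasts.** With Bonferroni over six and the same 5-year gap for all three duration groups, simulation (8,000 replicates per setting) gives 5.3 / 9.2% (n = 60) and 6.8 / 12.8% (n = 80). With no gap it gives 2.5% and 2.1%.

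**Step 4: sex.** Assume a 20-point difference in sex mix and a 0.3 SD sex effect: 0.20 × 0.3 = 0.06 SD. The uncorrected rate is then 6.2% (n = 60) or 6.7% (n = 80). A 30-point difference and a 0.4 SD effect give 0.12 SD, and 10.0% or 11.7%.

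**Step 5: masking.** Assume a true effect of 0.5 SD in the same direction as the age effect, with controls 5 years older. The apparent effect shrinks to 0.5 − 0.11 = 0.39 or 0.5 − 0.17 = 0.33 SD. Bonferroni power for one contrast falls from 52% to 20–30% (n = 60), or from 69% to 29–42% (n = 80).

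**Step 6: adjusted model.** A linear model with group, age and sex, simulated over gaps of 0 to 8 years, gives 4.5–5.3% uncorrected and 0.6–1.0% with Bonferroni for one contrast. Its mean estimate is within 0.003 SD of zero. In the masking setting its power is 53–56% (n = 60) or 69–72% (n = 80). At a 5-year gap its standard error is 0.178–0.183 SD against 0.182 unadjusted (n = 60), and 0.154–0.158 against 0.158 (n = 80).

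**The case against.** - **The contrast lies outside the stated aim.** This is true. The protocol states no hypothesis for it, and duration within diabetics needs no controls. That limits the weight of the point. Still, a full group of 60 to 80 people is recruited for this contrast, and the title rests on it.
- **Some comparability is built in.** Controls share the age floor, the ocular exclusions and the image-quality rules, and they come from the same department. This stands as far as it goes, but none of it equalises age above 40 or sex, and how controls are identified is still not stated.
- **A regression is planned, and age and sex are recorded.** The plan may therefore end up adjusting. It does not commit to doing so for this contrast.
- **The size is assumed.** This is correct. The documents give no age distribution, OCTA variability, or age or sex effect. A graded gap of 0, 2.5 and 5 years across the duration groups lowers the any-of-three rate with Bonferroni to 3.5–6.0% (n = 60) or 4.2–7.4% (n = 80).
- **A linear model ignores the non-parametric fallback.** The plan provides rank tests in case of non-normality. In a check with heavy-tailed outcomes, the adjusted model kept its error rate at about 5% with essentially unchanged standard errors, so this is no obstacle at these group sizes.

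**Conclusion.** The concern holds. Followed as written, the plan leaves the diabetic-versus-control contrast open to confounding by age and, to a lesser degree, sex.

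Under the assumptions above the harm is moderate at a 5-year age gap: roughly two to three and a half times the nominal error uncorrected, and more in relative terms with Bonferroni. It is slight at 2–3 years. The loss of power when controls are older can be larger. These figures show sensitivity to assumptions and do not estimate the bias this study will have.

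The matter should be fixed because the remedy is cheap. It does not threaten the stated aim. Confidence is medium, since the true imbalance is unknown.

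**What to change.** 1. State that controls meet inclusion criteria 1 and 3 and no exclusion criterion, have no known diabetes, and say where they are recruited.
2. For each OCTA parameter, report each duration group against controls from a linear model with group, age and sex (ANCOVA), with the planned Bonferroni correction. Make this the main result for the control contrast and keep the unadjusted tests as descriptive.
3. Tabulate age and sex by group.
4. Add recorded comorbid diseases in a sensitivity analysis.
5. Where feasible, balance controls on age and sex at recruitment. This is optional.

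**Cost.** Protocol wording and one more linear model per OCTA parameter, from data already recorded. No extra patients or tests are needed, and precision is essentially unchanged. Optional balancing would slow control recruitment a little.

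**Limits.** The model assumes a roughly linear age effect. It does not remove selection from the control source (for example, people attending an eye clinic for another reason), undiagnosed diabetes among controls, or other unmeasured confounding.

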One eye will be selected for inclusion from each patient. If both eyes from an individual patient are similar the right eye will be included in the study. The effect of eye motion-related artifacts is minimized using VTRAC eye tracking software [19].

Images to be included in the study will be required to have a signal strength greater than 7, minimal motion artifacts, decentralization from the foveal center of less than 20 μm , and minimal evidence of obscuration by media opacities [20].

Image analysis will be automatically performed by the AngioVue Comprehensive software, which will provide automated segmentation and calculation of retinal microvascular metrics such as FAZ-related and SVD. The analysis will include the inner retina between the inner limiting membrane and an anterior offset from the retinal pigment epithelium of 110 μm . The superficial capillary plexus (SCP) as the superficial 70% of the inner retina, and the deep capillary plexus (DCP) is the remaining 30% [21].

OCTA parameters derived from the SCP and DCP will be classified into two categories:

- (1) FAZ related metrics: FAZ area, FAZ perimeter and FAZ flow density (FD)
- (2) Vessel density-related metrics: superficial vessel density (SVD) and deep vessel density (DVD) in the 6 mm patch (6 mm diameter around the foveal center), 1 mm patch (1 mm diameter around the foveal center), and inner ring (1 mm patch excluding the FAZ) [9, 20].

Statistical Analysis

Statistical analysis will be performed using SPSS software 23 (SPSS, Inc., Chicago, IL, USA). The Shapiro–Wilk test will be used. Comparisons between groups will be made using the Kruskal–Wallis H test or one-way ANOVA test. Differences between two groups will be estimated with a Mann–Whitney U test or t-test. Multivariate linear regression models will be used to analyze potential associations between each OCTA parameter and systemic risk factors. All p values will be based on two-tailed testing and considered to be statistically significant if $p < 0.05$. A Bonferroni correction will be applied when appropriate.

References

- 2) Early Treatment Diabetic Retinopathy Study Research Group. Classification of Diabetic Retinopathy from Fluorescein Angiograms: ETDRS Report Number 11. *Ophthalmology* 1991, 98, 807–822.

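### Does the missing rule for choosing between two dissimilar eyes leave the comparison of duration groups open to biased selection?

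*Combined protocol and SAP*

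**What the plan says.** Under Procedure (Patients and Methods), the protocol states: "One eye will be selected for inclusion from each patient". The next sentence sends similar pairs to the right eye: "If both eyes from an individual patient are similar the right eye will be included in the study". These are the only two sentences on the choice of eye.

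Other parts of the same section bear on it indirectly:

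- The inclusion and exclusion criteria require a fundus free of macular edema and clinical retinopathy, and exclude ocular disease that could affect the retinal vessels.
- Duration of diabetes is taken in the history ("Medical history: including duration of DM, type of DM, use of DM medications, most recent hemoglobin A1C and presence of comorbid diseases") and then defines the groups ("Patients who meet the inclusion criteria will be divided into three groups depending on the duration of diabetes"). A non-diabetic control group is added.
- Imaging is described next ("OCTA images will be obtained for the patients by a comprehensive wide-field OCT device"), followed by the two eye-selection sentences.
- After those come the image limits ("Images to be included in the study will be required to have a signal strength greater than 7", with limits on motion, centration and media opacity), and then the measurement step: "Image analysis will be automatically performed by the AngioVue Comprehensive software".

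Sample size determination gives 60 to 80 eyes per group. Statistical Analysis compares the groups by Kruskal–Wallis or one-way ANOVA, then two groups at a time by Mann–Whitney or t-test, two-sided at 0.05. On multiplicity it adds: "A Bonferroni correction will be applied when appropriate".

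**The concern.** The rule depends on a comparison of the two eyes, but the basis of that comparison is not named. It could be fundus findings, scan quality or the OCTA values themselves. The eligibility criteria and image limits can remove an eye, but they cannot choose between two eyes that both pass. Automated software protects the measurement. It does not decide which eye's result is entered.

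The aim is to relate OCTA parameters to duration of diabetes, and the person choosing the eye may know that duration. If the more abnormal eye were preferred more often in long-duration patients than in the others, the group means would separate with no true effect. A reader of the results could not detect this, because the plan does not call for a record of why an eye was chosen.

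**Working it through.** **Reading the text.** There are three cases.

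1. Only one eye meets the criteria and image limits. The eye is settled.
2. Both qualify and are similar. The right eye is used.
3. Both qualify but are not similar. No rule is given.

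If similar means that both eyes qualify, case 3 is empty and the plan is complete. Under a narrower meaning, case 3 exists, and the document does not say how often it occurs.

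**Order of events.** Timing is not stated. Order on the page does not settle it either way: eye selection is described after history, grouping and imaging, but before the image limits and before the software computes the metrics.

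**Size if case 3 were misused.** The document has no figure on this point to reproduce, so what follows is an illustration and not a bound.

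Inputs:

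- Group size n = 60 to 80 (Sample size determination); two-sided alpha 0.05 (Statistical Analysis).
- Assumed, not in the document: the two eyes are bivariate normal with equal means, SD 1 and correlation ρ of 0.5 to 0.9. The worse eye is taken only in the most dissimilar share q of pairs (10% or 20%), in one group only. The right eye is used in all other pairs, as the plan says.

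The right-minus-left difference has SD √(2(1−ρ)). Taking the worse eye in a pair adds half the absolute difference to the pair mean. Averaged over the top share q, the shift in the group mean is

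shift = √(2(1−ρ)) × φ(z), where z is the 1 − q/2 normal quantile and φ the normal density.

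- q = 0.10: z = 1.645, φ(z) = 0.103. At ρ = 0.5 the shift is 1.000 × 0.103 = 0.103 SD; at ρ = 0.9 it is 0.447 × 0.103 = 0.046 SD.
- q = 0.20: z = 1.282, φ(z) = 0.175. At ρ = 0.5 the shift is 0.175 SD; at ρ = 0.9 it is 0.447 × 0.175 = 0.078 SD.

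The rejection rate under no true difference comes from a noncentral t with 2n − 2 degrees of freedom and noncentrality shift/√(2/n). If the eye is chosen on one metric and another is tested, the shift is multiplied by the correlation of the inter-eye differences, assumed to be 0.5.

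| Share of pairs | Eye chosen on | Shift (SD) | Error, n = 60 to 80 |
|---|---|---|---|
| 10% | tested metric | 0.05–0.10 | 5.7–9.9% |
| 10% | another metric | 0.02–0.05 | 5.2–6.2% |
| 20% | tested metric | 0.08–0.18 | 7.1–19.7% |
| 20% | another metric | 0.04–0.09 | 5.5–8.6% |
| Any share, same in all groups | either | difference 0 | 5% |

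If the correction were taken over all six pairs of the four groups (an assumption, since the plan does not specify it), the target per test is 0.05/6 = 0.83%. The tested-metric rows then become 1.0–2.4% at 10% and 1.4–6.2% at 20%. Bonferroni reduces the rate but does not remove the effect.

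A model that takes the worse eye in a random 20% or 50% of one group's patients gives 5.4–7.9% or 7.7–24.1%. It does not describe this gap, because random pairs include similar ones, which the rule already assigns to the right eye. Reaching those figures would mean breaking the written rule, not using its silence.

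**The case for a change.** The strongest case for a change is that clarification is cheap and has to come early. A right-eye default, decided without sight of the metrics or study group, takes two sentences and leaves eligibility, sample size and examinations as they are. Once eyes have been chosen, nobody can reconstruct why. The protocol's Introduction itself says that OCTA shows changes a clinical examination misses, so eyes that look alike on the fundus may differ on the scan. At the upper end of the illustration the error is nearly four times nominal.

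Much of this stands. The wording is incomplete, and a fixed rule would be tidier. But the upper figure needs several things at once: one eye in every five pairs picked on the very metric tested, always in the worse direction, in one group only, with an inter-eye correlation as low as 0.5. The plan lists several FAZ and vessel-density metrics, so one choice of eye cannot be tuned to all of them unless their inter-eye differences move together. The rates are also for a single two-group t-test, whereas the plan lists an overall four-group comparison first. Excluding clinical retinopathy and other relevant eye disease narrows the clinical differences that would make a pair dissimilar.

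**Conclusion.** The omission is real: similarity is undefined, and two qualifying but dissimilar eyes have no written rule. It does not call for a change. On the natural reading, the plan already uses the right eye whenever both qualify, and new text would only restate it. On a narrower reading, this is a gap that investigators would be expected to fill sensibly, with the right eye as the evident default.

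Bias requires selection that is both outcome-driven and different between groups. The document neither shows nor suggests this, and with equal selection the effect is nil. On the assumed inputs (ρ of 0.5 to 0.9, 10–20% of pairs in one group, 60 to 80 eyes per group), the error of one nominal 5% test would be 5.7–19.7% if the choice used the tested metric and 5.2–8.6% if it used another. The correlation, the shares and the 0.5 factor have no source in the document, so these ranges show what deliberate or careless misuse could do. They do not estimate what this study will do.

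### Signal strength is used only as an image-entry cut and enters no planned analysis, so a residual signal difference between groups could be reported as a duration effect on vessel density.

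*Combined protocol and SAP*

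**What the plan says.** All references are to the combined protocol and SAP.

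- **Image quality (Patients and Methods, Procedure).** "Images to be included in the study will be required to have a signal strength greater than 7, minimal motion artifacts". The same sentence limits decentration and requires "minimal evidence of obscuration by media opacities". The signal scale and its maximum are not stated, and minimal opacity is not graded.
- **Outcomes (same section).** "Vessel density-related metrics: superficial vessel density (SVD) and deep vessel density (DVD) in the 6 mm patch", and also in the 1 mm patch and the inner ring, together with FAZ metrics. All are computed automatically by the device software.
- **Groups.** Patients are "divided into three groups depending on the duration of diabetes: 0–5 years (short), 6–10 years (medium), and more than 10 years (long"), with a fourth, non-diabetic control group. On size, "every group would include from 60 to 80 eyes calculated by Yamane's formula".
- **Group tests (Statistical Analysis).** The overall test is given as "Comparisons between groups will be made using the Kruskal–Wallis H test or one-way ANOVA test". For any pair of groups, the plan then turns to simple two-sample methods: "Differences between two groups will be estimated with a Mann–Whitney U test or t-test".
- **Regression (Statistical Analysis).** The only adjusted model is described thus: "Multivariate linear regression models will be used to analyze potential associations between each OCTA parameter and systemic risk factors". The covariates are not listed.
- **Error control (Statistical Analysis).** Two-tailed tests at 0.05, with Bonferroni where appropriate; the family of tests is not defined.

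Nothing in the document plans to report signal strength by group, match on it, adjust for it or run a sensitivity analysis on it.

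**The concern.** By screening images on signal and media clarity, the protocol treats both as capable of spoiling the measurement. A cut narrows their variation but does not remove it: scans above 7 can still differ in signal, and some opacity is still allowed.

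A false duration effect needs two links:

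1. Among passing scans, measured vessel density falls as signal falls.
2. Passing scans have lower signal in longer-duration eyes, for example through lens opacity.

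Neither link is documented, so both are assumptions here. If both hold, the artefact lowers vessel density, which is also the early change that the Introduction describes in eyes without clinical retinopathy. The stated aim is the impact of duration on OCTA parameters, and the planned tests could not separate the two explanations. A larger sample would not help, because it makes a biased difference more likely to reach significance.

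The regression does not clearly close the gap. A scan property is not a systemic risk factor on a plain reading. Adjusting for age or HbA1c may remove part of a signal imbalance, but may not remove all of it.

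**Working it through.** **The plan's own figure.** The plan gives no number for signal bias, so there is none to reproduce. The group size of 60 to 80 is taken as stated; the values of N and e behind it are not given, and this point does not depend on them.

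**Inputs from the document**
- n = 60 or 80 eyes per group.
- Two-sided alpha 0.05.
- Four groups, hence 4 × 3 / 2 = 6 pairwise contrasts.

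**Assumptions, not in the document**
- Vessel density SD: 3 percentage points.
- Loss of density per unit of signal: 1 to 3 points.
- Difference in mean signal between two groups, above the cut: 0, or 0.25 to 0.5 units.
- Bonferroni family: the six pairwise contrasts, so alpha = 0.05 / 6 = 0.0083.

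**Step 1: artefact.** Artefact = slope × signal gap. The smallest non-zero case is 1 × 0.25 = 0.25 points and the largest is 3 × 0.5 = 1.5 points. With no gap it is 0.

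**Step 2: chance of a positive t-test with no true effect.** Let d = artefact / 3. The test statistic is noncentral t with 2n − 2 degrees of freedom and noncentrality d × √(n/2). For 1.0 point and n = 60: d = 0.333, noncentrality = 0.333 × √30 = 1.826, critical value 1.980, rejection probability 44.1%.

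| Artefact (points) | d | alpha 0.05, n = 60 / 80 | alpha 0.0083, n = 60 / 80 |
|---|---|---|---|
| 0 | 0 | 5.0% / 5.0% | 0.8% / 0.8% |
| 0.25 | 0.083 | 7.4% / 8.2% | 1.5% / 1.8% |
| 0.5 | 0.167 | 14.8% / 18.2% | 4.1% / 5.5% |
| 1.0 | 0.333 | 44.1% / 55.4% | 20.1% / 29.0% |
| 1.5 | 0.5 | 77.5% / 88.2% | 52.4% / 68.8% |

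The rates are per contrast. Bonferroni lowers them but leaves the biased estimate unchanged.

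**Step 3: how plausible is the top row?** Suppose passing scans score 8, 9 or 10 in equal shares (an assumption, since the scale is not stated). The signal variance is then 2/3. With total SD 3, a slope of b points per unit makes signal explain b² × (2/3) / 9 of the variance in density:
- b = 1: 7%
- b = 2: 30%
- b = 3: 67%

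The 1.5-point case needs the 67% slope together with the largest assumed gap, so it is an extreme. At the largest gap (0.5 units), the 1.0-point case needs b = 2.

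**Step 4: does the covariate work?** Four groups were simulated with no true group effect, 4,000 runs per setting. Signal scores were 8, 9 or 10; the control-to-long difference in mean signal was 0 to 0.75 units; the slope was 0.3 or 0.6 SD of density per unit.
- Signal balanced: the unadjusted tests stayed near nominal, at 4.3–5.4%.
- Largest gap and slope (bias 0.45 SD): unadjusted ANOVA was positive in 57.8% (n = 60) and 72.8% (n = 80) of runs, and the control-versus-long t-test in 70.5% and 82.7%.
- Signal added as a covariate: 4.3–5.5% in every setting.

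The simulation makes density linear in signal and signal exactly recorded, so it shows the covariate at its best. A coarse score could leave some bias.

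**The case against.** **The causal chain is not in the document.** This stands. A quality cut shows that the authors care about signal; it does not show a slope above the cut or an imbalance between groups. A reader might infer that any duration effect this study finds will be a scan-quality effect. The documents do not support that. They support only that the plan could not tell the two apart if signal were unbalanced.

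**The existing controls count for something.** This stands in part. Lens opacity is not named among the patient exclusions, and a reader might infer that it is uncontrolled. It is not: the image rule bars scans with more than minimal obscuration, the same rules apply to every group, and an anterior segment examination is planned. What remains is residual variation after two filters. They narrow the likely gap but do not show that it is zero.

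**Age adjustment could help.** This stands. It is tempting to say that adjusting for age or HbA1c cannot remove an instrument artefact. That does not follow: if signal differs because the groups differ in age, age adjustment removes the age-driven part. The tenable statement is that it may not remove all of it. The plan also neither lists age as a covariate nor matches on it.

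**FAZ metrics.** A reader might extend the point to say that low signal distorts FAZ measures in the direction of disease. Nothing in the document supports a direction, so the point is confined to vessel density.

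**The 5% figures are the least favourable reading.** This is fair, which is why the zero-gap and Bonferroni columns are shown. The Bonferroni family is itself an assumption.

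**Conclusion.** The omission is certain from the text: signal strength is an entry cut and nothing more. Confidence in it is high. The consequence is conditional, and confidence in it is medium. It requires lower signal in longer-duration eyes among passing scans and a residual slope of density on signal, and the document has data on neither.

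Under the stated assumptions, the chance of a false two-group difference runs from the nominal level when signal is balanced (5%, or 0.8% with Bonferroni over six contrasts) to 78–88% (52–69% with Bonferroni) at an extreme artefact of 1.5 points. These figures illustrate sensitivity and are not estimates for this study. The point justifies an inexpensive improvement to the analysis. It is not evidence that the design fails.

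**What to change.** Add to Statistical Analysis, before any analysis is run:

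1. Record the device's signal value for every included scan. It must already be read to apply the cut.
2. Tabulate signal strength by duration group and for controls.
3. Fit a regression for each OCTA parameter that includes duration group, with signal strength as a continuous covariate alongside the systemic factors.
4. Report the signal-adjusted duration estimate beside the unadjusted group test, and qualify any duration claim if the two disagree.

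The cost is one data column, one table row and one degree of freedom per model, with no new scan or patient. The adjusted effect may be smaller or less precise. If signal proves balanced, the table shows it and strengthens the result.
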